3.2. Group 2: Non-pregnant, non-lactating females of child bearing potential

Objectives	Endpoints
Primary	

 To evaluate the safety and tolerability of IH and IV oxytocin. 	
 General safety parameters: adverse events; absolute values and changes over time of vital signs (blood pressure, heart rate) and 12-lead electrocardiogram (ECG) parameters (PR, QRS, QT, Corrected QT interval [QTc] intervals) from pre-dose values. Specific respiratory safety parameters: adverse respiratory events as monitored by spirometry including Forced expiratory volume at 1 minute (FEV1.0), respiratory rate, and pulse oximetry.

 To characterize the pharmacokinetics of single doses of IH oxytocin and 5 I.U. IV oxytocin. 	
 Plasma concentration time profile for IH oxytocin and 5 I.U. IV oxytocin. PK parameters: C_{max}, C_{p10}, C_{p20}, C_{p30}, t_{max}, AUC, Plasma clearance (CL), volume of distribution and t_{1/2} will be calculated as data permit.
Exploratory	

 To evaluate endogenous plasma oxytocin concentrations in non-pregnant females in the presence and absence of the combined oral contraceptive. 	
 Pre-dose plasma concentrations of oxytocin.

 To compare the IH pharmacokinetics of oxytocin between Cohort A (subjects on combined oral contraceptive) and Cohort B (subjects using a non-hormonal form of contraception). 	
 C_{p10}, C_{p20}, C_{p30}, C_{max}, AUC(0-3h), Area under the concentration-time curve from time zero to infinity (AUC[0-∞]) and t_{1/2}, will be compared as data permit.

 To compare the IV pharmacokinetics of oxytocin between Cohort A and Cohort B. 	
 C_{max}, AUC, t_{1/2}, CL and Volume of distribution (VOD) will be compared as data permit.

[figure not shown]
3.3. Groups 1 and 2: Women in TSL and Non-pregnant, non-lactating females of child bearing potential

Objectives	Endpoints
Exploratory	

 To compare pharmacokinetics of IH oxytocin between Group 1 and Group 2. 	
 Cp10, Cp20, Cp30, Cmax, AUC(0-3h) AUC(0-∞), and t1/2 will be compared as data permit.

[figure not shown]
4. STUDY DESIGN

4.1. Overall Design

4.1.1. Study Schematic Group 1: Women in TSL

4.1.2. Study Schematic Group 2: Non-pregnant, non-lactating females of child bearing potential

4.1.3. Study Design Detail

This study will enrol two groups.

Group 1 - Women in TSL

Group 1 will enrol women with an uncomplicated pregnancy, and main phase procedures will occur during TSL. Subjects will be randomized to receive either IH or IM oxytocin

as active management of TSL. The specific timing of this dose will be as per local standard of care.¹

Group 2 - Non-pregnant, non-lactating females of child bearing potential

Group 2 will enrol healthy, non-pregnant, non-lactating female subjects of childbearing potential, and each subject will participate in 2 dosing sessions. Group 2 will be divided into two cohorts: Cohort A will enrol women on a combined oral contraceptive, and Cohort B will enrol women who are not using a hormonal form of contraceptive. Group 2 subjects will receive IH oxytocin at one dosing session, and IV oxytocin at the other dosing session; the order of IH versus IV oxytocin administration will be randomly assigned.

PK samples will be analysed periodically throughout the study duration to enable development of the population PK model and derivation of PK parameters via non-compartmental methods, as data permits.

No formal interim analysis is planned, however, PK samples will be analysed and preliminary PK parameters derived following completion of approximately 5 women on each treatment group: IH, IM in Group 1 and IH in Group 2 Cohort A in order to assess if dose escalation is required.

4.1.3.1. Pregnant Females (Group 1)

Subjects will review the study information and if they agree to participate, sign the informed consent form. For most subjects this is expected to take place at an outpatient antenatal visit, or additional study-specific screening visit. If a subject meets all inclusion/exclusion criteria for the study, she will be eligible for enrolment in the study.

To facilitate recruitment, and provide subjects ample time to consider participation, screening may occur any time after 18 weeks gestation (based on estimated date of delivery). See time and events (T&E) table in Section 7.1 for details.

4.1.3.2. Non-pregnant Females (Group 2)

Subjects will review the study information and if they agree to participate, sign the informed consent form. If a subject meets all inclusion/exclusion criteria for the study, she will be enrolled in the study.

Screening may occur within 28 days prior to randomization for non-pregnant volunteers. If a subject falls outside this window prior to randomization and enrolment, she must be re-screened. Certain screening procedures may not be required to be repeated; see T&E (Section 7.1) for details.

¹ For information only: Standard of care at proposed clinical site is to administer the oxytocic drug by IM injection with the birth of the anterior shoulder, or immediately after the birth of the baby and before the cord is clamped and cut.

Group 2 subjects will take part in 2 dosing sessions, which must be conducted a minimum of 48 hours apart. It is recommended that subjects complete Session 2 within 14 days of Session 1. Subjects will be randomized to receive either IH or IV oxytocin during Session 1, and to receive the other treatment during Session 2, such that all subjects in Group 2 receive both treatments over the course of the 2 sessions.

4.1.4. ROTHALER Inhaler Training

The investigator/designee will be trained to load the ROTACAPS powder capsule into the device, prime the dose and instruct the subjects to inhale from the ROTHALER inhaler in the appropriate manner (refer to Section 6.7). Subjects will be instructed by the investigator/designee to use an inspiration technique (2 inhalations) that enables maximal inhalation of the ROTACAPS powder capsule contents (refer to Section 6.7 for full details). This will ensure optimal and consistent drug delivery (full instructions available in the Study Reference Manual [SRM]).

4.1.5. Length of Stay for All Subjects

Group 1 - Women in TSL

Subjects in Group 1 will be admitted to hospital during labour as part of their routine care, and will be required to remain inpatient for a minimum of 4 hours after receiving any study-related dose of oxytocin. After final PK collection, subjects will be finished with study procedures and the main phase of the study will be considered complete. Discharge from hospital will be determined by the subject's medical provider.

Group 2 - Non-pregnant, non-lactating females of child bearing potential

Subjects in Group 2 will be admitted to the clinical unit prior to dosing on Day 1 and are to remain inpatient until at least 4 hours after dosing. Discharge will occur at the discretion of the investigator.

4.2. Treatment Arms and Duration

Screening	
Group 1: All screening assessments to be completed after the 18th week of pregnancy (based on estimated date of delivery)
 
Group 2: All screening assessments to be completed within 28 days prior to the first dose

Treatment Session	
Group 1: Each subject will take part in 1 dosing session.
 
Group 2: Each subject will take part in 2 dosing sessions

Treatment Arms ¹	
Group 1: Subjects will be randomised to receive one of the following study treatments:
 
 • 400 mcg IH oxytocin • 10 I.U. IM oxytocin 
Group 2: Subjects will receive both of the following study treatments over the course of two dosing sessions:
 
 • 400 mcg IH oxytocin • 5 I.U. IV oxytocin
Follow-up	
Group 1: Follow Up 1 – Within approximately 24 hours post dose.
 
Group 1: Follow Up 2 – At least 7 days and no greater than 14 days after study drug administration.
 
Both visits may be conducted in-person or via telephone. Group 2: At least 7 days and no greater than 21 days after last study drug administration.
 
This visit will be conducted in-person.
 
If warranted, additional follow-up visits may be scheduled for both Groups.

Total Duration	
Group 1: Screening after 18th week of pregnancy (i.e. within 168 days of 1 dosing session) + follow up of 7 - 14 days = approximately 183 days
 
Group 2: Screening within 28 days of dosing session 1 + 2 dosing sessions with a maximum of 14 days between dosing + follow-up of 7 – 21 days = 64 days

¹ See Section 6.4 for possible dose adjustment to IH oxytocin.

4.3. Type and Number of Subjects

Sufficient subjects will be screened such that approximately 20 subjects complete all study procedures in Group 1, and approximately 10 subjects complete all study procedures in Group 2 (approximately 5 in each cohort of Group 2). Refer to Section 6.3 for treatment assignment information.

If subjects prematurely discontinue the study, additional replacement subjects may be recruited and assigned to the same treatment at the discretion of the Sponsor. Replacement subjects will complete all study procedures as outlined in Section 7.1.

If the PK variability between subjects in Group 1 is higher than expected, it may be required to increase the sample size up to a maximum of 10 additional subjects per treatment group for IH and IM. In the event of this, sufficient subjects will be screened such that a maximum of 50 subjects complete Group 1.

If a dose adjustment is required in either group, additional subjects may be recruited such that a full 10 subjects receive the final IH or IV dose. See Section 6.4.1 for more details.

4.4. Design Justification

Group 1 - Women in TSL

This trial uses a randomized, single-dose approach to assign women in TSL to receive oxytocin by one of two routes: IM or IH. No placebo is being used, as the current standard of care is to administer oxytocin as active management of TSL to prevent PPH.

Group 2 - Non-pregnant, non-lactating females of child bearing potential

A group of non-pregnant, non-lactating women of childbearing potential will receive IH and IV oxytocin. This group will be divided into two cohorts: Cohort A will enrol women on the combined oral contraceptive. This cohort will serve as a control group, as they most closely resemble the population enrolled in the FTIH study. Cohort B will enrol women using a non-hormonal form of contraception. This comparison group will help characterize the effect of oral contraceptives on endogenous oxytocin production and the PK profile of oxytocin.

Blinding

This study uses an open-label design.

4.5. Dose Justification

Single inhaled doses of oxytocin (50-600 mcg) have been generally well tolerated in the FTIH study, with no emerging safety signals, in healthy, non-pregnant, premenopausal female subjects (Study 201558) [GlaxoSmithKline Document Number 2016N277949_00; see also Section 2.2.1]. Following inhaled administration oxytocin was rapidly absorbed into the systemic circulation (t_{max} ranging from 0.05 to 0.50 h) with systemic exposure (C_{max} and AUC) increasing with inhaled dose in an

[figure not shown]
approximately proportional manner between 200 and 600 mcg. In general, the shape of the observed oxytocin concentration-time profile following inhaled administration was consistent with that following IM administration.

Based on the data from the FTIH study, and assuming that the PK characteristics of IH and IM oxytocin are similar in TSL compared with non-pregnant women, the 400 mcg inhaled dose is predicted to be an effective dose in women in TSL by ensuring that the systemic exposure (Cp10, Cp30 and AUC(0-3 h)) following IH dosing is at least that following IM administration at the approved dose of 10 I.U. This would be based on the adjusted geometric mean ratio (90% Confidence Interval [CI]) treatment comparisons for Cp10, Cp30 and AUC (0-3 h) following 400 mcg IH compared with 10 I.U. IM, namely 1.10 (0.85, 1.43), 1.65 (1.30, 2.09) and 1.27 (1.07, 1.50) respectively in study 201558. The PK parameters (Cp10, Cp30 and AUC(0-3 h)) have been selected to ensure onset and duration of action of the IH product is at least comparable to IM.

The clinical safety and reported AEs with oxytocin correlates to C_{max}, with the C_{max} of 10 I.U. IV representing the upper bounds of what could be considered safe in current clinical practice (AEs include flushing, which can cause a transient decrease in blood pressure and reflex tachycardia; see the Oxytocin Summary of Product Characteristics for more information). The recommendation in the United Kingdom (UK) in clinical practice has been to reduce the IV dose to 5 I.U. IV or administer by a controlled IV infusion [Bolton, 2003].

Minimising the risk of high C_{max} levels of oxytocin following the IH administration is therefore important. Based on a comparison of model predicted systemic exposure following IV administration to non-pregnant, premenopausal female subjects with observed PK profiles following 400 mcg IH oxytocin, it is anticipated that C_{max} following administration of the 400 mcg dose will not markedly exceed values following 5 I.U. IV bolus oxytocin (Figure 2). The inclusion of the 5 I.U. IV dose will allow an assessment of the potential safety and PK of the inhaled formulation compared to IV route of administration.

Figure 2 Model predicted profiles (median (95%PI)) following IM (10 I.U. and IV bolus (5 I.U. administration of oxytocin overlaid with observed plasma concentrations of oxytocin following 400 mcg IH oxytocin to healthy non-pregnant females

Whilst published literature on the PK of oxytocin in non-pregnant and pregnant women is limited there is some evidence to suggest that the metabolic clearance of oxytocin may increase during pregnancy. This may be related to degradation by the circulating aminopeptidase, oxytocinase, and/or pregnancy-related changes in hepatic and renal function [Syntocinon, 2014; Thornton, 1990]. In addition, there may be circulating levels of endogenous oxytocin in the plasma in women in TSL [Thornton, 1988] and increases in blood volume (40-50%) and total body water [Costantine, 2014]. As a result of these pregnancy related changes, systemic exposure to oxytocin may differ between healthy non-pregnant women and women in TSL for a given dose and route of administration of oxytocin. However, given that any pregnancy-related changes in systemic clearance, and/or distribution and baseline oxytocin levels, are considered to equally impact on each route of administration (IV, IM and IH), it is considered that the relative ratio of IV to IM and IH exposure observed in non-pregnant women is likely to be maintained in pregnancy. The only exception may be if pregnancy results in marked changes in absorption profiles. However, in a study of inhalation profiles of non-pregnant and women in the third stage of labour, the inhalation endpoints appeared to be broadly similar across the two cohorts and any small changes are not considered to markedly impact the delivery of an inhaled product in the third stage of labour [GlaxoSmithKline

Document Number [2015N239682_00](#)]. In addition, in a pre-clinical sheep model the ratio IH:IV was generally similar in non-pregnant and post-partum ewes (Data on file Monash). In the event of enhanced pulmonary absorption in pregnancy, the selected 400 mcg inhaled dose is predicted to have an approximate 2-fold safe cover for Cmax compared with an 10 I.U. IV bolus oxytocin (assumes linearity from 5 -10 I.U. IV).

4.6. Benefit:Risk Assessment

Summaries of findings from both clinical and non-clinical studies conducted with GR121619 can be found in the Investigator's Brochure [GlaxoSmithKline Document Number [2015N240749_01](#)] and oxytocin for parenteral administration [[Syntocinon](#), 2014]. The following section outlines the risk assessment and mitigation strategy for this protocol:

4.6.1. Risk Assessment

Potential Risk of Clinical Significance	Summary of Data/Rationale for Risk	Mitigation Strategy
Investigational Product (IP) – Inhaled Oxytocin – GR121619		
Bronchospasm, cough and dyspnoea, with increased theoretical risk in asthmatic subjects.	Oxytocin receptors are known to be expressed in human bronchial smooth muscle and up regulated by interleukin (IL)-13. Therefore, there is a hypothetical risk of bronchospasm, cough and dyspnoea.	See Section 5.2 for exclusion criteria. The oxytocin summary of product characteristics (SPC) does not list asthma as a contraindication to administration. Symptomatic wheezing may be treated with bronchodilator at the discretion of the investigator. Forced expiratory volume at 1 minute (FEV1) monitoring for both paradoxical and oxytocin induced bronchospasm Subjects with asthma or known pulmonary disease are excluded.
Hypotension, tachycardia and prolongation of QTc interval	Transient flushing, hypotension and tachycardia could be observed if the IH PK profile is comparable to an IM or IV oxytocin profile. Effects of oxytocin on the Cardiovascular system (CVS) is unclear and contradictory in	Ongoing assessments of study subjects' cardiovascular function including blood pressure (BP), heart rate (HR) and ECG. Only single-dose IH, IM, or 5 IU IV bolus injection routes of administration will be used

Potential Risk of Clinical Significance	Summary of Data/Rationale for Risk	Mitigation Strategy
	
the literature but IV administered oxytocin can have a vasodilatory and negative inotropic effect in humans. Hypotension is thought to arise as a result of vascular smooth muscle relaxation and oxytocin binding to cardiac atrial OTR which leads to atrial natriuretic peptide (ANP) being transiently released into the systemic circulation.
 
Prolongation of the QTc interval has been reported at the time of caesarean delivery with 10 IU IV oxytocin administration, rather than IM injection, in susceptible individuals
	
as study treatment. Telemetry and frequent 12-lead ECGs will be used to monitor the healthy subject cohorts
 
The 5 IU IV dose of oxytocin is the standard dose administered at the Rosie Maternity hospital post Caesarean Section.
 
IV bolus will be given as a slow IV injection over 30 seconds with the option to change to a 5 minute infusion if frequent CV adverse effects are observed
 
Exclusion of subjects with long QT syndrome, congenital cardiac abnormalities, and subjects taking anti-arrhythmic drugs.
 
12-lead ECG and telemetry covering Cmax in healthy subjects administered IH, IM and IV oxytocin

Insufficient uterotonic effect	The altered physiology and pharmacokinetics of women in the TSL may lead to a sub-optimal dose of inhaled oxytocin, resulting in a reduced or absent uterotonic effect.	
In this setting, women in TSL and post-delivery are intensively observed. Therefore, any adverse events, including excessive blood loss due to unenhanced uterine contraction, will be managed in accordance with current local practice guidelines. This will usually include administration of additional uterotonic agents in the first instance.
 
A follow-up within 24 h of discharge by the study team will be performed to specifically enquire if any late bleeding problems had occurred.

Potential Risk of Clinical Significance	Summary of Data/Rationale for Risk	Mitigation Strategy
		An interim analysis of IH and IM PK in the TSL group will be performed to ensure that the PK is in the acceptable range for efficacy to be anticipated.
Reference Intervention - IM Oxytocin / IV Oxytocin		
Hypotension, tachycardia and prolongation of QTc interval	See above section.	See above section. Subjects receiving the IV Oxytocin are required to have a systolic BP \geq 90 Millimeter of mercury (mmHg) prior to dosing.
Myocardial Ischaemia and ST change on ECG	ECG changes consistent with myocardial ischaemia have been observed with 10 IU oxytocin IV bolus in healthy women associated with hypotension and tachycardia.	Oxytocic cardiovascular effects appear to be transient and persistent myocardial damage very rare and associated with 10 IU IV. Study is only using 5 IU IV as a slow IV bolus which is associated with a short lived increase in heart rate and reduction in BP but not ST changes on ECG in women undergoing Caesarean Section. Telemetry and 12-lead ECG monitoring in healthy subjects.
Abdominal pain	There is a hypothetical risk that IM oxytocin may trigger abdominal pain through contractions of the non-pregnant uterus in healthy women. Given the short half-life of oxytocin (approximately 30 minutes), the duration of a single abdominal pain episode would be expected to be brief, not sustained and not	This is a theoretical possibility and not expected to occur. Ongoing assessments of study subjects' well-being along with vital signs and laboratory evaluations will be completed throughout the duration of the study. Abdominal pain which is clinically uncomfortable to the subject may be treated with paracetamol at the local investigator's discretion.

Potential Risk of Clinical Significance	Summary of Data/Rationale for Risk	Mitigation Strategy
	recurrent in the absence of further oxytocin administration. Furthermore, no abdominal pain was observed in the FTiH study.	

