
 To compare the IH pharmacokinetics of oxytocin between Cohort A (subjects on combined oral contraceptive) and Cohort B (subjects using a non-hormonal form of contraception). 	
 C_{p10}, C_{p20}, C_{p30}, C_{max}, AUC(0-3h), Area under the concentration-time curve from time zero to infinity (AUC[0-∞]) and t_{1/2}, will be compared as data permit.

 To compare the IV pharmacokinetics of oxytocin between Cohort A and Cohort B. 	
 C_{max}, AUC, t_{1/2}, CL and Volume of distribution (VOD) will be compared as data permit.

Groups 1 and 2 – Women in TSL and Non-pregnant, non-lactating females of child bearing potential

[figure not shown]
Objectives	Endpoints
Exploratory	

 To compare pharmacokinetics of IH oxytocin between Group 1 and Group 2 	
 Cp10, Cp20, Cp30, Cmax, AUC(0-3h) AUC(0-∞), and t1/2 will be compared as data permit.

Overall Design

Group 1 – Women in TSL

Group 2 – Non-pregnant, non-lactating females of child bearing potential

Treatment Arms and Duration

Screening	
Group 1: All screening assessments to be completed after the 18th week of pregnancy (based on estimated date of delivery).
 
Group 2: All screening assessments to be completed within 28 days prior to the first dose.

Treatment Session	
Group 1: Each subject will take part in 1 dosing session.
 
Group 2: Each subject will take part in 2 dosing sessions.

Treatment Arms ¹	
Group 1: Subjects will be randomised to receive one of the following study treatments:
 
 • 400 micrograms (mcg) IH oxytocin • 10 I.U. IM oxytocin 
Group 2: Subjects will receive both of the following study treatments over the course of two dosing sessions:
 
 • 400 mcg IH oxytocin • 5 I.U. IV oxytocin
Follow-up	
Group 1: Follow Up 1 – Within approximately 24 h post dose.
 
Group 1: Follow Up 2 – At least 7 days and no greater than 14 days after study drug administration.
 
Both visits may be conducted in-person or via telephone.
 
Group 2: At least 7 days and no greater than 21 days after last study drug administration.
 
This visit will be conducted in-person.
 
If warranted, additional follow-up visits may be scheduled for both Groups.

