7. STUDY ASSESSMENTS AND PROCEDURES

Protocol waivers or exemptions are not allowed with the exception of immediate safety concerns. Therefore, adherence to the study design requirements, including those specified in the Time and Events Table, are essential and required for study conduct.

This section lists the procedures and parameters of each planned study assessment. The exact timing of each assessment is listed in the Time and Events Table in Section 7.1.

The following points must be noted:

- If assessments are scheduled for the same nominal time, THEN the assessments are recommended to occur in the following order:
 1. 12-lead ECG
 2. vital signs
 3. blood draws

Note: The timing of the assessments should allow the blood draw to occur at the exact nominal time.

- The timing and number of planned study assessments, including safety, pharmacokinetic, pharmacodynamic, immunogenic or other assessments may be altered during the course of the study based on newly available data (e.g., to obtain data closer to the time of peak plasma concentrations) to ensure appropriate monitoring.
- The change in timing or addition of time points for any planned study assessments must be documented in a Note to File which is approved by the relevant GSK study team member and then archived in the study sponsor and site study files, but this will not constitute a protocol amendment.
- The Institutional Review Board (IRB)/ Independent Ethics Committee (IEC) will be informed of any safety issues that require alteration of the safety monitoring scheme or amendment of the Informed Consent Form.
- No more than 500 mL of blood will be collected over the duration of the study, including any extra assessments that may be required.

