7.1. Time and Events Table**7.1.1. Time and Events Table – General Overview****Group 1**

Procedure	Study Day			
	Screening ⁴	Main Phase	Follow – Up 1 (approx. 24 hours post dose)	Follow – Up 2 (7-14 days post dose)
Informed Consent and Demography	X			
Brief Physical Examination	X			
Medical history (incl. substance abuse)	X			
Inhaler device training / education session	X			
Laboratory assessments ¹	X			
Vital signs ²	X	X		
Pharmacokinetic blood sample		X		
Oxytocin Administration (IM/IH)		X		
Full blood count		X		
Labour Events Documentation		X		
Device acceptability questionnaire ³		X		
Prior / concomitant medication review	X	X	X	X
AE review		----- continuous review -----		
SAE review		----- continuous review -----		

1. Only required if done as part of routine care. Additional study-specific laboratory assessments not required.
2. Includes blood pressure, heart rate, temperature, respiratory rate
3. Only to be used when randomized to IH oxytocin
4. To be completed after 18th week of pregnancy (based on estimated date of delivery).

Group 2

Procedure	Study Day		
	Screening ⁵	Main Phase	Follow - Up (7-21 days post dose)
Informed Consent and Demography	X		
Brief Physical Examination	X	X	
Medical history	X		
Pregnancy test	X	X	
Alcohol Breath Test, Smokerlyzer, Urine Drug Screen ¹	X	X	
HIV, Hep B and Hep C screen ²	X		
Inhaler device training / education session	X		
Laboratory assessments (including liver chemistries)	X	X	
Immunogenicity sample		X	X
12-lead ECG	X ⁴	X	
Cardiac Telemetry		X	
Vital signs ³	X	X	
Spirometry (FEV-1) ⁴	X	X	
Admission to unit		X	
Pharmacokinetic blood sample	X	X	
Oxytocin Administration (IH or IV)		X	
Prior / concomitant medication review	X	X	X
AE review		----- continuous review -----	
SAE review	----- continuous review -----		
Discharge from unit		X	

1. Smokerlyzer at PI/designee discretion if smoking history in question.
2. If test otherwise performed within 3 months prior to first dose of study treatment, repeat testing at screening is not required.
3. Includes blood pressure, heart rate, temperature, respiratory rate, and SpO2.
4. Performed in triplicate.
5. To be completed within 28 days of randomization.

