7.3. Safety

Planned time points for all safety assessments are listed in the Time and Events Table (Section 7.1). Additional time points for safety tests (such as vital signs, physical exams and laboratory safety tests) may be added during the course of the study based on newly available data to ensure appropriate safety monitoring.

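### Section 4.6.1 requires a late-bleeding contact within 24 h of discharge, but the schedule ties Follow-Up 1 to the dose, so a woman discharged after Follow-Up 1 has no scheduled contact in that window

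*Protocol*

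**What the plan says.** In the protocol's risk table (Section 4.6.1), the row on insufficient uterotonic effect falls under inhaled oxytocin. Besides close observation after delivery, its mitigations include this commitment: "A follow-up within 24 h of discharge by the study team will be performed to specifically enquire if any late bleeding problems had occurred".

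The follow-up schedule uses a different anchor:

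- Synopsis (Section 1): "Follow Up 1 – Within approximately 24 h post dose".
- Section 4.2: "Follow Up 1 – Within approximately 24 hours post dose".
- Group 1 table in Section 7.1.1: "Follow – Up 1 (approx. 24 hours post dose".
- Follow-Up 2 is at 7 to 14 days after study drug (Section 4.2).

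On length of stay, Section 4.1.5 sets a minimum of 4 h after the dose and no maximum: "Discharge from hospital will be determined by the subject's medical provider".

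On which text governs, Section 7 says "The exact timing of each assessment is listed in the Time and Events Table in Section 7.1" and describes the study design requirements, "including those specified in the Time and Events Table, are essential and required for study conduct". Section 7.3 adds "Planned time points for all safety assessments are listed in the Time and Events Table (Section 7.1".

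**The concern.** One stated safeguard has two clocks. Section 4.6.1 starts its 24 h at discharge; the schedule starts its 24 h at the dose. They agree only when the woman has already gone home by the time Follow-Up 1 is made. If she is still an inpatient then, Follow-Up 1 cannot ask about bleeding after discharge, and the schedule contains no other contact tied to discharge.

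Sites are told to take timing from the Time and Events Table. At Follow-Up 1, the Group 1 table shows medication review and the continuing AE and SAE review. It lists neither a post-discharge contact nor a specific bleeding enquiry. For such a woman the safeguard depends on the site acting on a sentence in the risk table. Otherwise the study first asks about post-discharge bleeding at Follow-Up 2, although Section 7.3.2 makes postpartum haemorrhage and placental problems adverse events of special interest.

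**Working it through.** The protocol gives no figure to reproduce here, so the check is a timeline.

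**Inputs (hours post dose)**

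- Discharge, D: at least 4, no upper limit (Section 4.1.5).
- Follow-Up 1, F: within approximately 24 (Sections 1 and 4.2), or approximately 24 (Section 7.1.1).
- Follow-Up 2: 7 × 24 = 168 to 14 × 24 = 336 (Section 4.2).
- Window set by Section 4.6.1: from D to D + 24.

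**Step 1: when does Follow-Up 1 meet Section 4.6.1?** It must satisfy D ≤ F ≤ D + 24. Since D is at least 4, the upper end is at least 28 h, so a contact at around 24 h does not overrun it. The binding condition is D ≤ F, meaning she must already be discharged when the contact is made. With F = 24 and D = 4, the contact comes 24 − 4 = 20 h after discharge; with D = 24, it comes 0 h after. Both meet the requirement.

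**Step 2: what if D is later than F?** Follow-Up 1 then precedes discharge. Follow-Up 2 can fall inside the window only if 168 ≤ D + 24, that is D ≥ 144 h (day 6). For any discharge after F and before 144 h, no scheduled contact lies in the 24 h after discharge.

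**Step 3: how long is the wait?** The gap from discharge to Follow-Up 2 runs from 168 − D to 336 − D. The discharge times below are illustrative; the protocol gives none.

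| Discharge, D | Gap in hours | Gap in days |
|---|---|---|
| 36 h | 132 to 300 | 5.5 to 12.5 |
| 48 h | 120 to 288 | 5.0 to 12.0 |
| 72 h | 96 to 264 | 4.0 to 11.0 |

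Section 4.6.1 promises at most 1 day.

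**Step 4: how firm is the 24 h boundary?** It is not sharp. Because Sections 1 and 4.2 say within approximately 24 h, a site could make Follow-Up 1 earlier, before the discharge of a woman who goes home inside the first day. Equally, a contact slightly after 24 h could still catch a woman discharged at about that time. What matters is whether discharge comes after the Follow-Up 1 contact, not whether it comes after hour 24.

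**The case against.** The strongest reply is that the two texts do not exclude each other. Section 4.6.1 is itself an instruction, nothing in Section 7 forbids an extra call, and a site can make Follow-Up 1 at about 24 h and telephone again after discharge. That stands: a reader might infer that the protocol rules the contact out, and it does not. The defect is that the schedule, which the protocol says sets the timing, does not contain the contact.

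A second reply is that the protocol has room for it. Section 4.2 allows further follow-up visits if warranted, Section 7 lets the timing and number of assessments change by Note to File on newly available data, and Section 7.3 lets safety time points be added on the same basis. All three exist, so it would be wrong to say that the schedule offers no way to add the call. All three are discretionary, however, and none guarantees a contact that Section 4.6.1 states without condition.

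A third reply is that the women concerned are those observed longest. They are under hospital care until discharge, they still receive Follow-Up 1, AE review continues throughout, and bleeding reported at Follow-Up 2 is still recorded. This is correct and limits the consequence: what is lost is a timely, specific enquiry, not the recording of events. But Section 4.6.1 lists close observation and the post-discharge enquiry as separate mitigations, so the first does not replace the second.

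Finally, Group 1 is restricted to uncomplicated pregnancies at low risk of haemorrhage, and no length of stay is given. The documents do not show that any woman will stay past Follow-Up 1.

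**Conclusion.** The point holds as a mismatch between a stated safeguard and the schedule meant to deliver it. Any Group 1 woman discharged after her Follow-Up 1 contact, and before about day 6, has no scheduled contact in the 24 h after discharge. The wait to the next one is several days, for example 5.5 to 12.5 days after a discharge at 36 h.

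The size of the problem is modest. The number of women affected cannot be derived from the protocol and may be zero. The waits assume the illustrative discharge times and Follow-Up 2 inside its stated window. PK results, dose decisions and sample size are unaffected.

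A reader might also infer that Section 4.6.1 promises this enquiry in both arms. It does not: the row concerns inhaled oxytocin, so for the intramuscular arm the same contact is a recommendation, not something the protocol already requires.

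**What to change.** Keep Follow-Up 1 at about 24 h post dose. In the synopsis, Section 4.2 and the Group 1 table of Section 7.1.1, add a telephone contact within 24 h after discharge for any woman not yet discharged at Follow-Up 1. In the table, list the bleeding enquiry from Section 4.6.1 at that contact, or at Follow-Up 1 if she has already gone home.

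Section 4.6.1 requires this for the inhaled arm. Doing it in the intramuscular arm as well is advisable, so that bleeding is ascertained equally in the two randomised arms.

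Rewording Section 4.6.1 to match Follow-Up 1 would remove the inconsistency, but it would also drop the post-discharge enquiry for exactly these women, so it is the weaker repair.

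The cost is at most one telephone call per affected woman, and Section 4.2 already allows Group 1 follow-up by telephone. PK sampling, PK analyses and sample size do not change.
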